Potential participants will be screened by telephone and have the study explained to them in detail. If they qualify and choose to participate they will come in for the first of three visits. Informed consent will be obtained and demographic information collected. Information requested on the demographic form includes ethnicity, income, education, marital status, smoking and alcohol use, and exercise habits. Next they will have blood pressure checked and if not within parameters they will be dropped from the study and informed that they need to follow up the abnormal result with their health care provider. They will receive \$20.00 partial compensation for their time. Next a finger stick blood glucose check will be done to rule out diabetes. If their result falls out of the specified parameter range they will be dropped from the study and informed that they need to follow up the abnormal result with their health care provider. They will receive \$20.00 partial compensation for their time. Those that pass these screening tests will have 15 to 25 cc's of peripheral blood (serum) collected by the study coordinator via venipuncture while at rest. They will then stretch for 2 minutes (60 seconds marching in place followed by 10 toe touches) followed by accelerating treadmill walking exercise. The exercise intervention will consist of a 15 minute period of walking on a treadmill. The treadmill will not be inclined during the intervention. The participants target heart rate will be determined by deducting their age from 220. They will start walking on the treadmill at a speed of 1.7 mph and the speed will be titrated as indicated to keep their heart rate at 50 to 90% of target. Heart rate will be monitored via the pulse oximetry feature of the Welch Allyn vital signs monitor. Blood pressure will be measured every 3 minutes during the exercise intervention and until they have returned to baseline (within 10 points) following cessation of the exercise protocol. The test will be stopped for any participant complaint of chest pain, excess fatigue, difficulty breathing, a blood pressure reading of more than 180/94, or a participant request. If symptoms increase or do not completely resolve with 15 minutes of rest the study coordinator will call 911 (through campus police) to activate the EMS response. If symptoms resolve completely within 15 minutes participants will be withdrawn from the study and advised to follow up with their health care provider. Any participant unable to complete the exercise intervention for any reason will be withdrawn from the study.

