
The exercise intervention is no more intense than what most participants would encounter walking during their normal day-to-day activities. The participants will be closely monitored and the intervention stopped for any subjective or objective evidence of discomfort. Participants involved in this study will have been screened for any medical conditions that would increase their risk of any negative effects from the exercise intervention.

Five to fifteen minutes after the exercise intervention has been completed blood will again be collected in exactly the same manner as the resting sample. Participants will then receive a 2 week supply of either NutraStem or placebo and will be advised to take one tablet every morning and evening before meals for the next 2 weeks. Participants will be advised to bring their empty pill containers to their next session so we can confirm they are taking the supplement as required. Those that complete the 1st session will receive \$40.00 compensation. If the participant is unable to complete any portion of the visit activities at any visit they will be withdrawn from the study due to their

inability to complete the study. All visit activities will be recorded in detail on the visit session record.

The second visit will occur 2 weeks later and include a blood pressure check, an at rest blood draw, the exercise intervention, and then a repeat blood draw five to fifteen minutes after completion of the intervention. Participants will then receive a 2 week supply of either NutraStem or placebo and will be advised to take one tablet every morning and evening before meals for the next 2 weeks. Participants will be advised to bring their empty pill containers to their next session so we can confirm they are taking the supplement as required. If the blood pressure is outside of the specified range they will be dropped from the study and no blood collection or study intervention will take place. They will receive \$20.00 compensation for the visit. Those that complete the 2nd session will receive \$60.00 compensation.

The third visit will be the same as the second visit. If the session cannot be completed due to failed blood pressure screen participants will receive \$20.00. All participants that complete the 3rd session will receive \$80.00.

SESSION	ACTIVITIES	VISIT LENGTH	COMPENSATION

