Exercise will consist of 2 minutes of stretching/warm up consisting of marching in place for 60 seconds followed by 10 toe touches. The exercise intervention will consist of a 15 minute period of walking on a treadmill. The treadmill will not be inclined during the intervention. The participants target heart rate will be determined by deducting their age from 220. They will start walking on the treadmill at a speed of 1.7 mph and the speed will be titrated as indicated to keep their heart rate at 50 to 90% of target. Heart rate will be monitored via the pulse oximetry feature of the Welch Allyn vital signs monitor. Blood pressure will be measured every 3 minutes during the exercise intervention and until they have returned to baseline (within 10 points) following cessation of the exercise protocol. The test will be stopped for any participant complaint of chest pain, excess fatigue, difficulty breathing, a blood pressure reading of more than 180/94, or a participant request. If symptoms increase or do not completely resolve with 15 minutes of rest the study coordinator will call 911 (through campus police) to activate the EMS response. If symptoms resolve completely within 15 minutes participants will be withdrawn from the study and advised to follow up with their health care provider. Any participant unable to complete the exercise intervention for any reason will be withdrawn from the study.

The exercise intervention is no more intense than what most participants would encounter walking during their normal day to day activities. The participants will be closely monitored and the intervention stopped for any subjective or objective evidence of discomfort. Participants involved in this study will have been screened for any medical conditions that would increase their risk of any negative effects from the exercise intervention.

Data Analysis/Data Monitoring

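### The exercise heart rate (50 to 90% of 220 minus age) and the post-exercise draw (5 to 15 minutes) need not match across a participant's visits, which adds avoidable noise to the post-exercise cell counts.

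*Combined protocol and SAP*

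**What the plan says.** The objective, stated just before section B, concerns the supplement together with an exercise stimulus. Under Blood Analysis in section E, CD34+ and CD133+ cells are measured at every draw, so three of a participant's six samples follow the walk.

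Section E (visit 1) and the Exercise stimulus subsection give the same intensity rule:

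- "The participants target heart rate will be determined by deducting their age from 220"
- "the speed will be titrated as indicated to keep their heart rate at 50 to 90% of target"

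Some elements are fixed: "The exercise intervention will consist of a 15 minute period of walking on a treadmill", with no incline and a starting speed of 1.7 mph.

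On timing, section E says for visit 1: "Five to fifteen minutes after the exercise intervention has been completed blood will again be collected in exactly the same manner as the resting sample". Visit 2 has "a repeat blood draw five to fifteen minutes after completion of the intervention", and "The third visit will be the same as the second visit".

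Section E describes the intensity in general terms: "The exercise intervention is no more intense than what most participants would encounter walking during their normal day-to-day activities". It also says that visit activities are recorded in detail on the visit session record, without naming speed, heart rate or draw time. Data Analysis/Data Monitoring specifies repeated measures ANOVA and gives no role to achieved intensity or draw time.

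**The concern.** The walk is the provocation and the post-exercise count is its readout. For that count to show change from visit 1 to visits 2 and 3, the provocation and the sampling time should be much the same on each occasion. The plan fixes duration, slope and starting speed, but speed is then adjusted to a wide heart-rate band and the draw has a ten-minute window. No sentence links visits 2 and 3 to what the same participant did at visit 1. The remark about collecting blood in the same manner concerns how the sample is taken, and its own sentence contains the 5-to-15-minute window.

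A 60-year-old could be walked near 80 bpm with a 15-minute draw at visit 1 and near 140 bpm with a 5-minute draw at visit 3, and both visits would follow the plan. At stake is precision in a trial of at most 30 per arm. If heart rate, speed and draw time are not recorded, they cannot be recovered later.

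**Working it through.** The plan states no sample-size derivation, variance or effect size, so it has no figure of its own to reproduce.

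**1. Permitted heart rate.** Inputs: target = 220 − age; limits 0.50 and 0.90 of target (section E and Exercise stimulus); ages 50 to 70 (section F).

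| Age | Target | 0.50 × target | 0.90 × target | Width |
|---|---|---|---|---|
| 50 | 170 | 85 | 153 | 68 bpm |
| 60 | 160 | 80 | 144 | 64 bpm |
| 70 | 150 | 75 | 135 | 60 bpm |

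The ratio of the limits is 0.90 / 0.50 = 1.8 at every age.

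**2. Permitted draw time.** 15 − 5 = 10 minutes of spread, at each of the three visits.

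**3. What draw timing could do (assumed half-lives).** If the exercise-induced rise decayed with half-life h, a draw 10 minutes later would hold 2^(−10/h) of it, and a draw 2 minutes later 2^(−2/h).

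| h (min) | 10 minutes later | 2 minutes later |
|---|---|---|
| 10 | 50% | 87% |
| 20 | 71% | 93% |
| 30 | 79% | 95% |
| 60 | 89% | 98% |

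For draw times spread evenly over the window, the CV of the increment is about 20%, 10%, 7% and 3% respectively.

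**4. What intensity could do (worst case, assumed).** Suppose the rise is proportional to heart rate above rest, rest is 40 to 45% of the 220 − age figure, and visits are spread evenly over the whole band. The excess over rest then runs from 10 to 50 points (mean 30) or from 5 to 45 points (mean 25). The SD is 40/√12 = 11.5 in both cases, so the CV is 0.38 or 0.46. These CVs describe the increment only. If exercise raises the count by a fraction g of the resting level (also assumed), the CV of the post-exercise count is g × CV / (1 + g):

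- g = 10%: about 4%
- g = 20%: 6 to 8%
- g = 50%: 13 to 15%
- g = 100%: 19 to 23%

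**5. What added variance would cost (illustration).** Assume 30 per arm, two-sided alpha 0.05 and the standardised difference giving 80% power: (1.960 + 0.842) × √(2/30) = 0.723. If uncontrolled stimulus and timing add a fraction r to the outcome variance, power = Φ(2.802/√(1 + r) − 1.960), and the n per arm that restores 80% is 30 × (1 + r).

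| r | Power | n per arm for 80% |
|---|---|---|
| 10% | 76% | 33 |
| 25% | 71% | 38 (37.5 rounded up) |
| 50% | 63% | 45 |
| 100% | 51% | 60 |

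The documents do not say which row applies.

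**6. Descriptions of the walk, side by side.** Section E and Exercise stimulus specify no incline. The screening script tells callers that the slope goes up at three-minute intervals. The Risk/Benefit Assessment in section G refers to the Modified Bruce protocol. The 90% upper limit also sits awkwardly with the statement that the walk is no harder than everyday walking, which sets no numerical limit.

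**The case against.** The trial is randomised, double-blinded and placebo-controlled. A blinded coordinator's drift should fall on both arms alike, so the between-arm comparison is protected in expectation. This stands. A reader might infer that no post-exercise result could be told apart from changes in how the walk was run; the design does not support that for the randomised comparison. It has more force for change over visits within one arm, where drift and a time effect look the same.

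The three resting samples do not depend on the walk, so part of the evidence on cell levels is untouched. This also stands.

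Fixed duration, slope, starting speed and mode may keep practice well inside the band. That is possible, but none of them fixes intensity once speed is titrated, and the slope is not described consistently. The example visits show what is allowed, not what is expected.

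A reader might also infer that the lower limit amounts to no exercise at all. The documents give no resting heart rates, so this cannot be shown.

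Finally, the visit session record may already capture these variables. The form is not in the available text, so its fields cannot be judged; the protocol text simply does not name them.

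**Conclusion.** The concern holds as a matter of precision. The plan permits a 1.8-fold range of exercise heart rate and a ten-minute range of draw time, and requires neither to match across a participant's visits. That much follows directly from the text.

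The expected consequence is avoidable within-person noise in the post-exercise CD34+ and CD133+ counts, with within-arm change more exposed than the between-arm contrast. Bias between arms is not the expected result, given randomisation and maintained blinding. The size is unknown. The illustrative CVs are worst-case, apply to the exercise-induced increment, and rest on assumed dose-response, resting rate, response size and half-life; the power figures rest on assumed added variance. At the mild end (a long half-life, a small exercise response) the loss could be trivial. The improvement is worth making because it is nearly free.

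**What to change.** **Section E, post-exercise draw.** Add that at visits 2 and 3 each participant's post-exercise draw is taken at the same minute after exercise as at visit 1 (for example within 2 minutes), always inside the existing 5-to-15-minute window. A draw that misses the narrower interval is flagged and kept in the analysis.

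**Visit session record.** Name the fields: treadmill speed and heart rate at each existing 3-minute blood pressure reading, and the clock times of exercise end and draw.

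**Data Analysis/Data Monitoring.** Report achieved heart rate, speed and draw time by arm and visit. Pre-specify a sensitivity analysis of the post-exercise counts that uses them. It should be supportive only, because these variables arise after randomisation.

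**Stimulus across visits.** The sponsor should state whether and how the exercise stimulus is to be kept comparable across a participant's visits within the existing heart-rate and stop rules. Simply repeating visit-1 speeds could collide with the rule that speed is titrated to heart rate, so this is left to the sponsor.

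**Reconcile the text.** Bring into agreement the no-incline statements (section E, Exercise stimulus), the rising slope in the screening script, the Modified Bruce reference in section G, and the 50 to 90% band against the everyday-walking statement.

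**Cost.** A few sentences and a few fields on an existing form, with no new equipment, staff or blood. The downside is that a draw may occasionally miss the narrower interval and be flagged.

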VISIT 1	informed consent, demographic information collected, BP screening, diabetes screening, resting blood draw, exercise intervention, post exercise intervention blood draw, receive NutraStem or placebo	40 to 80 minutes	\$40.00 * \$20.00 if unable to complete session for any reason
Visit 2	resting blood draw, exercise intervention, post intervention blood draw	45 minutes	\$60.00 * \$20.00 if unable to complete session for any reason
Visit 3	resting blood draw, exercise intervention, post intervention blood draw,	45 minutes	\$80.00 * \$20.00 if unable to complete session for any reason

Blood Analysis:

A 10ml Lavender top with EDTA tube of collected blood will be processed for MNC's and designated for flow cytometry to measure the stem cells including CD34+ and CD133+ cells at all blood draw time points. [name] will complete this portion of the analysis. A 5 ml SST tube will be collected for a lipid panel on the 1st blood draw of each session and delivered by the coordinator to Quest Lab for analysis. One additional tube of 5 cc's will be processed for serum measurements of biomarkers of inflammation and oxidative stress by the sponsor. These measures (IL1 β , IL4, IL6, hsCRP) will be completed by the sponsor. De-identified serum samples will be stored by [name] lab in a locked -80 freezer on the 5th floor of CBH until the sponsor specified time points of the study and then shipped to the sponsor following IATA Dangerous Goods Regulations by [name] lab personnel.

Blood sample collection tubes will be pre-labeled by the pharmacist doing the study drug/placebo randomization. The following randomization system will be used for the samples collected during this study:

Identifier (randomized to active ingredient or placebo)	Subject number	Study	Visit	Blood Draw	Description of Blood Draw
JKSB	01	01	01		Pre-exercise
JKSB	02	02	02		Post-exercise
JKSB	03	03	01		Pre-exercise
JKSB	03		02		Post-exercise
JKSB	04			01	Pre-exercise
				02	Post-exercise

Therefore, subject 17 on visit 3 for the post-exercise blood draw would be coded as:
JSKB170302

Subject 5 for visit 1 and pre-exercise blood draw would be coded as:
JSKB050101

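### A walk stopped at visit 2 removes the person from the whole study, so a scheduled week-4 resting sample that needs no exercise is lost (low priority, cheap to change)

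*Combined protocol and SAP*

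**What the plan says.** The withdrawal rule for the treadmill walk appears twice, in section E (Experimental Design and Methods) and again under Exercise stimulus: "Any participant unable to complete the exercise intervention for any reason will be withdrawn from the study". Reasons for stopping include fatigue and the participant's own request, as well as chest pain, breathing difficulty and "a blood pressure reading of more than 180/94". Full recovery does not keep the person in: "If symptoms resolve completely within 15 minutes participants will be withdrawn from the study and advised to follow up with their health care provider".

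The visit 1 description in section E makes the rule general: "If the participant is unable to complete any portion of the visit activities at any visit they will be withdrawn from the study". The Screening script adds that a person whose blood cannot be collected at any visit is dropped.

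Product is first handed out at the end of visit 1, after the walk and the second draw. Visit 2 comes two weeks later and runs in the order pressure check, resting draw, walk, post-exercise draw, second supply. For week 4, "The third visit will be the same as the second visit".

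Under Blood Analysis, flow cytometry is used "to measure the stem cells including CD34+ and CD133+ cells at all blood draw time points". For lipids, "A 5 ml SST tube will be collected for a lipid panel on the 1st blood draw of each session", which is the resting draw. The serum tube for inflammation and oxidative-stress markers is not tied to one draw.

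Data Analysis/Data Monitoring names repeated measures ANOVA with Scheffé post-hoc tests. It gives no analysis set, no missing-data rule and no report of withdrawals by arm.

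**The concern.** The protocol does not separate stopping the exercise from leaving the study. At visit 1 the two can reasonably coincide, because no product has been given. At visit 2 they should not. The person has taken product or placebo for two weeks, and whatever stopped the walk arose during that time. Withdrawal then removes someone from the randomised comparison because of an event after treatment began, and it cancels a blood draw that was already scheduled and requires no walking.

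What is at stake is the week-4 resting comparison: resting stem-cell counts, serum markers and the lipid panel. As written, it is restricted to people who tolerated the week-2 walk. The post-exercise response of a stopped session is lost whatever the rule says.

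**Working it through.** **The rule followed visit by visit**

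- Visit 1: the walk precedes dispensing, so a stop cannot be due to product. Withdrawal is reasonable.
- Visit 2: the resting draw has been taken and two weeks of product used. Withdrawal cancels both week-4 draws. The resting one does not depend on the walk.
- Visit 3: the resting draw comes before the walk, so a stop does not prevent it. The documents do not say whether samples from a withdrawn person are analysed.

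No other text keeps a withdrawn person for later sampling.

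**How many samples**

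The maximum is 60 people, 30 per arm (section E). No stop rate is given. If 5%, 10% or 20% stopped at visit 2 (assumed), the loss would be 60 × 0.05 = 3, 60 × 0.10 = 6 or 60 × 0.20 = 12 week-4 resting samples.

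**Power with withdrawal**

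The plan has no power figure to reproduce. Assumptions: two-sided 5% test of the week-4 resting value, adjusted for a baseline with correlation ρ = 0.6, and an effect d = 0.589 SD, chosen to give 80% power at 30 per arm. Power comes from the noncentral t distribution with 2n − 3 degrees of freedom and

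ncp = d / √(1 − ρ²) × √(n/2).

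Here √(1 − 0.36) = 0.8 and 0.589 / 0.8 = 0.736.

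| n per arm | ncp | power |
|---|---|---|
| 30 | 0.736 × √15 = 2.85 | 80.0% |
| 28 | 0.736 × √14 = 2.75 | 77.2% |
| 27 | 0.736 × √13.5 = 2.71 | 75.6% |
| 25 | 0.736 × √12.5 = 2.60 | 72.2% |

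**Power if the same people are kept**

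A person stopped during the visit-2 walk has not yet received the second supply, so may be about two weeks off product at week 4. Let f be the share of the effect that remains in such people. With two per arm affected, all analysed as assigned, the average effect is d × (28 + 2f)/30.

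| f | ncp | power |
|---|---|---|
| 0 | 2.85 × 28/30 = 2.66 | 74.4% |
| 0.5 | 2.85 × 29/30 = 2.76 | 77.3% |
| 1 | 2.85 | 80.0% |

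Withdrawal gives 77.2%. Ignoring the small change in degrees of freedom, the two are equal when (28 + 2f)/30 = √(28/30) = 0.966, so f = 0.49. Keeping people raises power only if product continues or about half the effect persists.

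**Bias**

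The mean in those who remain differs from the full-arm mean by (stop rate) × (gap between completers and stoppers). With the same gap in both arms, the bias in the treatment difference is gap × (difference in stop rates). Equal rates give 0. Assumed rates of 10% v 5% with a gap of 0.5 SD give 0.5 × 0.05 = 0.025 SD. Assumed rates of 15% v 5% with a gap of 1 SD give 0.10 SD.

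**The case against.** The strongest defence is that this is a deliberate and cautious rule. The stated aim is product combined with an exercise stimulus, and a person who can no longer walk cannot supply the week-4 exercise response. The study is run by a nurse coordinator, and dropping people after chest pain or raised pressure is conservative. Stops should also be rare: the protocol describes the walk as comparable to everyday walking, and anyone who could not manage it at visit 1 has already left. All of this stands. It is why the point is low priority and why the stopping criteria should not change. It does not explain why a resting draw that a clinician judges safe should be cancelled, particularly after a stop for fatigue or by request.

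A second objection is that a late sample from someone off product may mislead. That also stands in part: such a value says little about four weeks of dosing, and the working shows it can lower power. The answer is to record product status at week 4, not to discard the person.

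Three stronger readings are tempting, and the documents do not support them:

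- A reader might infer that the treatment comparison is biased. That needs stops, or their link to the outcome, to differ by arm. The documents give little reason to expect it, since they describe low ingredient doses.
- A reader might infer that keeping these people restores full power. The second supply is given only after the visit-2 post-exercise draw, so that cannot be assumed.
- A reader might infer that the samples already taken are thrown away as well, because classical repeated measures ANOVA usually drops incomplete series. The plan does not say how incomplete series are handled.

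**Conclusion.** The point holds as a low-priority, inexpensive improvement. The text is clear that a visit-2 stop ends participation and that the week-4 resting draw goes with it, for people already two weeks into treatment.

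The size cannot be fixed from the documents. On the assumed effect and correlation, two people lost per arm costs about 3 points of power (80.0% to 77.2%). Keeping them gives between 74.4% and 80.0%, depending on how much effect remains. The case for change is therefore mainly that the resting comparison keeps people in the arm to which they were assigned and uses samples already drawn. A power gain is possible but not assured.

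Two neighbouring matters are separate, and the point does not rest on them. One is the pressure screen at visits 2 and 3, under which "they will be dropped from the study and no blood collection or study intervention will take place". The other is the mismatch between two-week dispensing in section E and the four-week supply promised in the Screening script.

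**What to change.** 1. In section E and under Exercise stimulus, limit study withdrawal for an incomplete walk to visit 1, before product is dispensed.
2. After a visit-2 stop, end exercise for that person, record the reason and keep the samples already drawn. If the investigator judges it safe, invite the person to visit 3 for the resting draw only.
3. Make matching changes to the any-visit withdrawal sentence in section E and to the Screening script rule that drops people whose blood cannot be collected, so that neither undoes step 2.
4. Record whether the person is on or off product at week 4. If the investigator allows product to continue, state when the second supply is given.
5. In Data Analysis/Data Monitoring, analyse resting outcomes by assigned arm with a mixed model that keeps partial series. Treat missed post-exercise values as missing, and report stops by arm.

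The cost is a short amendment and a few lines of analysis text. The visit table already sets $20 for an incomplete session. The consent form, which is not in the file, may need a matching change. The investigator takes on a safety judgement for each return visit, and the data will include a few resting values without a post-exercise pair, some of them off product.

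### A treadmill test stopped for safety cuts that visit's payment to $20, a penalty on the symptom reports that most stop triggers depend on

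*Combined protocol and SAP*

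**What the plan says.** **Payment.** The visit table in section E (Experimental Design and Methods) gives $40, $60 and $80 for visits 1, 2 and 3. Each of its three rows adds that the amount is $20 "if unable to complete session for any reason". The narrative before the table attaches $20 only to failed screening: blood pressure or glucose at visit 1, blood pressure at visits 2 and 3. In the text available, the table alone sets the payment for a stopped exercise test.

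**Stopping.** Section E gives the stop rule twice, in the visit 1 description and under Exercise stimulus: "The test will be stopped for any participant complaint of chest pain, excess fatigue, difficulty breathing, a blood pressure reading of more than 180/94", or at the participant's request. A participant whose symptoms clear within 15 minutes is still withdrawn. More generally, "Any participant unable to complete the exercise intervention for any reason will be withdrawn from the study".

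**Safeguards.** Section E promises close monitoring and a stop for discomfort that is either felt or observed. Section G (Potential Risks) has a registered nurse coordinator watching, who may stop the test on her own judgement.

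**What participants hear.** The screening script states the full amount for completing each visit, and $20 for an abnormal screening result at visit 1 or a failed blood collection at any visit. It does not say what is paid when the treadmill test is stopped.

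**The concern.** The main protection during exercise is that the test stops when the participant feels unwell. Under the table, the participant who says so loses part of that visit's pay, and the loss is the same whether the stop was for chest pain or for convenience. The loss within the visit also grows from visit to visit. Payment and safety rule therefore pull in opposite directions at the moment when a prompt report matters most. What is at stake is the reliability of the symptom report as a safety control. No estimate, test or sample size depends on it.

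**Working it through.** There is no stated statistical figure to reproduce. The check is arithmetic on the payment schedule and a count of the stop triggers.

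**Inputs.** Full payments $40, $60 and $80, and incomplete-session payment $20 (visit table, section E). Withdrawal after any incomplete exercise (section E). Up to 60 participants (section E).

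**Step 1: loss within the visit.** Full payment minus $20, as a share of the full payment.

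- Visit 1: 40 − 20 = $20; 20/40 = 50%.
- Visit 2: 60 − 20 = $40; 40/60 = 67%.
- Visit 3: 80 − 20 = $60; 60/80 = 75%.

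**Step 2: total loss against a completer, and what remains if the visit is paid in full.** A completer receives 40 + 60 + 80 = $180.

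| Stop at | Received now | Loss now | Received if visit paid in full | Loss then |
|---|---|---|---|---|
| Visit 1 | $20 | $160 (89%) | $40 | $140 (78%) |
| Visit 2 | 40 + 20 = $60 | $120 (67%) | 40 + 60 = $100 | $80 (44%) |
| Visit 3 | 40 + 60 + 20 = $120 | $60 (33%) | $180 | $0 |

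The remaining $140 and $80 are payments for later visits that a withdrawn participant does not attend. They follow from the withdrawal rule, not from the $20 clause.

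**Step 3: stop triggers.** In both section E lists there are five: three reported symptoms, one blood-pressure limit and one participant request. Four of five start with the participant. The section G list also has five: two reported symptoms, participant request, blood pressure and coordinator judgement. Three of five start with the participant. The lists differ: excess fatigue appears only in section E, and coordinator judgement only in section G. They must be reconciled.

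**Step 4: cost of paying the stopped visit in full.** Extra cost per stop is $20, $40 or $60, depending on the visit. The documents give no stop rate, so two are assumed.

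- 10% of 60 = 6 stops: 6 × $20 = $120 to 6 × $60 = $360.
- 20% of 60 = 12 stops: 12 × $20 = $240 to 12 × $60 = $720.

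For scale, 60 completers cost 60 × $180 = $10,800.

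**The case against.** **The payment section may contain an exception.** The text under H. Payment/Compensation and the consent form were not available for this check, so an exception for safety stops cannot be excluded. If one exists, it contradicts the unqualified wording of the visit table, which would still need amending.

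**Not everything depends on self-report.** This stands and limits the concern. Blood pressure is taken every 3 minutes, heart rate is monitored, observed discomfort stops the test, and the nurse coordinator can stop it herself. But no heart-rate stop limit is listed, and early chest pain or fatigue may show no outward sign between readings.

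**The exercise is mild.** Section E likens it to everyday walking. It also allows 50 to 90% of 220 minus age, which is up to 0.9 × 170 = 153 beats per minute at age 50 and 0.9 × 150 = 135 at age 70. Section E has no incline, whereas the screening script describes a grade that rises every three minutes. Those passages must be reconciled.

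**The sums are small, and nobody is shown to have hidden a symptom.** Both are true. A reader might infer that the plan pays people to conceal chest pain. The documents support only that it penalises reporting; they contain no evidence of intent or of under-reporting.

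**The data are not shown to be affected.** A reader might also infer distorted stem-cell results or understated tolerability counts. The documents support neither. The payment rule is the same in both arms of a randomised, double-blind comparison, treadmill speed is titrated to heart rate whether or not symptoms are voiced, and the Data Analysis section defines no tolerability or stop-count analysis.

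**Conclusion.** The point holds as a matter of participant payment and safety. As written, the visit table penalises a safety stop by $20, $40 or $60 at the visit itself, while four of the five section E triggers rely on the participant speaking up. Objective monitoring and nurse judgement reduce the risk without removing the penalty.

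It would be tempting to quote the $160 (89%) lost at visit 1 as the size of the problem. That overstates what the clause does: $140 of it is pay for visits not attended, and only $20 comes from the $20 rule. At visit 2 the split is $80 and $40; at visit 3 the whole $60 comes from the rule.

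The conclusion assumes that the visit table governs payment and that neither section H nor the consent form overrides it. It does not depend on any assumed stop rate; only the cost estimate does. This is a cheap improvement, not a threat to the trial's inference.

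**What to change.** Amend the section E narrative and visit table, and align the screening script, section H and the consent form, as follows:

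- Pay the visit's full amount when exercise was started and then stopped for a symptom, for a blood-pressure reading or at the participant's request.
- Tell participants before the test that stopping does not reduce that visit's payment.
- Keep the existing $20 for visits that end before exercise: screen failures at visit 1, blood-pressure failures at visits 2 and 3, and failed resting blood draws.
- Leave the stop and withdrawal rules as they are for the purpose of this change.

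The cost is a wording amendment plus $20 to $60 per stop, in total about $120 to $720 over the assumed 10 to 20% stop rates. Some participants could stop early without penalty; the reason for each stop can be entered in the visit session record that section E already requires. The change removes only the same-visit penalty. Pay for later visits is still lost through withdrawal.
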